5.2.1 Inclusion Criteria

1. Adult male or female, ≥ 18 and ≤ 75 years old at Screening.

2. Atopic dermatitis with a diagnosis confirmed by a dermatologist (according to the Hanifin and Rajka criteria); and also onset of symptoms at least 1 year prior to baseline.
3. Moderate to severe AD defined by an EASI ≥ 16 , BSA $\geq 10\%$ and an IGA score ≥ 3 at the Baseline visit.
4. Documented history (within 1 year prior to the screening visit) of inadequate response to treatment with topical corticosteroids (TCS), or topical calcineurin inhibitors (TCI), or for whom topical treatments are otherwise medically inadvisable (e.g., because of important side effects or safety risks).
5. Twice daily use of an additive-free, bland emollient for at least 7 days prior to Baseline.
6. A negative serum pregnancy test for all female subjects at the Screening Visit and a negative urine pregnancy test for all female subjects of childbearing potential at the Baseline Visit prior to administration of first dose of study drug. Note: subjects with borderline pregnancy test at Screening must have a serum pregnancy test ≥ 3 days later to document continued lack of a positive result.
7. If female, subject must be postmenopausal OR permanently surgically sterile OR for Women of Childbearing Potential practicing at least one protocol specified method of birth control (Section 5.2.4), that is effective from the Baseline visit through at least 30 days after the last dose of study drug.

If male and subject is sexually active with a female partner(s) of childbearing potential, he must practice the protocol specified contraception from the Baseline visit through at least 30 days after last dose of study drug (Section 5.2.4).

Additional local requirements may apply. Refer to [Appendix P](#) for local requirements in Canada.

8. Subjects must voluntarily sign and date an informed consent, approved by an Independent Ethics Committee (IEC)/Institutional Review Board (IRB), prior to the initiation of any screening or study-specific procedures. For subjects in Japan

only: if a subject is under 20 years of age, then the subject and their parent or legal guardian must voluntarily sign and date an informed consent.

Rationale for Inclusion Criteria

- | | |
|-------|--|
| 1 – 5 | To select the appropriate subject population |
| 6 – 7 | The impact of ABT-494 on pregnancy and reproduction is unknown |
| 8 | In accordance with harmonized Good Clinical Practice (GCP) |

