5.2.4 Contraception Recommendations

Contraception Recommendation for Females

A woman who is postmenopausal or permanently surgically sterile (bilateral oophorectomy, bilateral salpingectomy or hysterectomy) is not considered to be a woman of childbearing potential and is not required to follow contraception recommendations.

Postmenopausal is defined as:

- Age \geq 55 years with no menses for 12 or more months without an alternative medical cause; or
- Age < 55 years with no menses for 12 or more months without an alternative medical cause AND a follicle-stimulating hormone (FSH) level > 40 IU/L.

If the female subject is < 55 years of age:

AND has had no menses for \geq 12 months AND has no history of permanent surgical sterilization (defined above), FSH should be tested at Screening.

- If FSH is not tested, it is assumed that the subject is of childbearing potential and protocol-specified contraception is required.
- If the FSH is tested and the result is consistent with post-menopausal status, contraception is not required.

- If the FSH is tested and the result is consistent with pre-menopausal status, contraception is required, and a serum pregnancy test must be performed (see Section 5.3.1.1 pregnancy test).

For a female subject at any age:

- Female subjects with menses within the past 12 months are of childbearing potential and FSH is therefore not required but contraception is required.
- Female subject who are surgically sterile (defined above) are not of childbearing potential and therefore no FSH testing or contraception is required.

A woman who does not meet the definition of postmenopausal or permanently surgically sterile is considered of childbearing potential and is required to practice at least one of the following highly effective methods of birth control that is effective from Study Day 1 (or earlier) through at least 30 days after the last dose of study drug.

- Combined (estrogen and progestogen containing) hormonal contraception (oral, intravaginal, transdermal) associated with the inhibition of ovulation, initiated at least 30 days prior to Baseline Visit.
- Progestogen-only hormonal contraception (oral, injectable, implantable) associated with inhibition of ovulation, initiated at least 30 days prior to Baseline Visit.
- Bilateral tubal occlusion/ligation (Japan only: bilateral tubal ligation only).

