- Vasectomized partner(s) provided the vasectomized partner has received medical confirmation of the surgical success and is the sole sexual partner of the women of childbearing potential trial participant.
- Intrauterine device (IUD).
- Intrauterine hormone-releasing system (IUS).
- True abstinence: Refraining from heterosexual intercourse when this is in line with the preferred and usual lifestyle of the subject (periodic abstinence e.g., calendar, ovulation, symptothermal, post-ovulation methods] and withdrawal are not acceptable).

If required per local practices, male or female condom with or without spermicide OR cap, diaphragm or sponge with spermicide should be used in addition to one of the birth control methods listed above (excluding true abstinence).

Additional local requirements may apply. Refer to [Appendix P](#) for local requirements in Canada.

Contraception Recommendation for Males

For a male subject who has a female partner who is postmenopausal or permanently sterile, no contraception is required.

A male subject who is sexually active with female partner(s) of childbearing potential must agree from Study Day 1 through 30 days after the last dose of study drug to practice contraception with:

- Condom use and female partner(s) using at least one of the contraceptive measures (as defined in the protocol for female study subjects of childbearing potential).
- OR
- True abstinence: Refraining from heterosexual intercourse-when this is in line with the preferred and usual lifestyle of the subject. (Note: Periodic abstinence [e.g., calendar, ovulation, symptothermal, post-ovulation methods] and withdrawal are not acceptable).

Additionally, male subjects must agree not to donate sperm from the Baseline Visit through 30 days after the last dose of study drug.

Male subjects are responsible for informing his partner(s) of the risk of becoming pregnant and for reporting any pregnancy to the study doctor. If a pregnancy occurs, a partner authorization form requesting pregnancy outcome information will be requested from the pregnant partner.

It is important to note that contraception recommendations described above are specifically intended to prevent pregnancy during exposure to the investigational therapies.

Additional local requirements may apply. Refer to [Appendix P](#) for local requirements in Canada.

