Appendix P. Local Canada Requirements

Section 5.2.1, Inclusion Criteria

10. If female of childbearing potential, must be practicing at least two reliable methods of contraception (one highly effective method combined with one effective method, refer to Section 5.2.4), that are effective from Study Day 1 through at least 30 days after the last dose of study drug.
11. If male, and subject is sexually active with the female partner(s) of childbearing potential, he must agree, from Study Day 1 through 30 days after the last dose of study drug, to practice the protocol-specified contraception (refer to Section 5.2.4).

Section 5.2.4, Contraception Recommendations

Contraception Recommendation for Females

A woman who is postmenopausal or permanently surgically sterile (bilateral oophorectomy, bilateral salpingectomy or hysterectomy) is not considered to be a woman of childbearing potential and is not required to follow contraception recommendations.

Postmenopausal is defined as:

- Age \geq 55 years with no menses for 12 or more months without an alternative medical cause; or
- Age $<$ 55 years with no menses for 12 or more months without an alternative medical cause AND an FSH level $>$ 40 mIU/L.

A woman who does not meet the definition of postmenopausal or permanently surgically sterile is considered of childbearing potential and is required to use two forms of contraception. This includes one form of highly effective contraception and one effective method of contraception. That is effective from Study Day 1 (or earlier) through at least 30 days after the last dose of oral study drug.

- Highly effective methods:
 - Hormonal contraceptives started at least 2 months prior to randomization (e.g., combined [estrogen and progestogen containing] [oral contraceptives, patch, vaginal ring, injectables, and implants]);
 - Intrauterine device (IUD) or intrauterine system (IUS);
 - Vasectomy and tubal ligation.
- Effective methods:
 - Barrier methods of contraception (e.g., male condom, female condom, cervical cap, diaphragm, contraceptive sponge)

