 - Note: The proper use of diaphragm or cervical cap includes use of spermicide and is considered one barrier method. The cervical cap and contraceptive sponge are less effective in parous women. The use of spermicide alone is not considered a suitable barrier method for contraception. When used consistently and correctly, "double barrier" methods of contraception (e.g., male condom with diaphragm, male condom with cervical cap) can be used as an effective alternative to the highly effective contraception methods described above. Male and female condoms should not be used together as they can tear or become damaged.

Contraception Recommendation for Males

For a male subject who has a female partner who is postmenopausal or permanently sterile, no contraception is required.

A male subject who is sexually active with female partner(s) of childbearing potential must agree from Study Day 1 through 30 days after the last dose of oral study drug to practice contraception with:

- Condom use and female partner(s) using at least one of the highly effective contraceptive methods (as defined in the protocol for female study subjects of childbearing potential).

Additionally, male subjects must agree not to donate sperm from Study Day 1 through 30 days after the last dose of oral study drug.

Male subjects are responsible for informing his partner(s) of the risk of becoming pregnant and for reporting any pregnancy to the study doctor. If a pregnancy occurs, a partner authorization form requesting pregnancy outcome information will be requested from the pregnant partner.

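### Appendix P (Canada) contradicts itself and the main protocol on whether double-barrier contraception can stand in for a highly effective method

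*Protocol*

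**What the plan says.** **Appendix P, items under Section 5.2.1.** Item 10 asks a woman of childbearing potential for two methods, described as "one highly effective method combined with one effective method". Item 11 covers male subjects.

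**Appendix P, text under Section 5.2.4.** The two-method rule is repeated: "This includes one form of highly effective contraception and one effective method of contraception". Hormonal methods, IUD or IUS, and vasectomy and tubal ligation are listed as highly effective. Barrier methods are listed only as effective. The note under the barrier list says that double-barrier combinations, used consistently and correctly, "can be used as an effective alternative to the highly effective contraception methods described above". The rule for male subjects asks for condom use plus a partner using a highly effective method.

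**Main body.** Inclusion criterion 7 (Section 5.2.1) requires at least one method from Section 5.2.4. There, a woman of childbearing potential "is required to practice at least one of the following highly effective methods of birth control". Where local practice calls for a condom, cap, diaphragm or sponge, it "should be used in addition to one of the birth control methods listed above". Both sections send the reader to Appendix P for Canada and describe the local requirements as additional.

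**The concern.** One appendix gives two answers on double barrier, and the more permissive one accepts something that the main body does not. Two Canadian sites reading the same pages in good faith could decide differently on the same woman.

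The stakes are safety and consistent eligibility. The rationale for the exclusion criteria (Section 5.2.2) says that the drug is teratogenic in rats and rabbits and that its impact on pregnancies is unknown. Treatment lasts up to 88 weeks. There is a data consequence too. Protocol Section 7.0 gives entry of a subject who did not meet the criteria as an example of a protocol deviation, and SAP Section 7.4 counts such subjects. Under Section 5.4.1, an eligibility violation found after dosing leads to withdrawal if the sponsor's medical or scientific director judges that continuing would put the subject at risk. Without one rule, it is unclear whether a site that followed the note has committed a deviation.

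**Working it through.** No arithmetic applies to the contradiction. The check takes one test case through each rule: a Canadian woman of childbearing potential whose only contraception is a male condom with a diaphragm, a combination that the note itself gives as an example.

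| Text applied alone | Requirement | Test case |
|---|---|---|
| Appendix P, item 10 | one highly effective and one effective method | not met |
| Appendix P, two-form sentence | the same | not met |
| Main criterion 7 with Section 5.2.4 | at least one listed highly effective method | not met |
| Appendix P, note | double barrier may stand in for the highly effective methods | accepted for that part |

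The third row rests on a count of the methods in main Section 5.2.4: combined hormonal, progestogen-only, tubal occlusion or ligation, vasectomised partner, IUD, IUS and true abstinence. That makes seven, and none is a barrier.

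The next step combines the texts, because a site has to apply them together. Two questions are open: whether items 10 and 11 replace criterion 7 or add to it, and what the note satisfies.

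1. **The appendix adds to the main body.** Criterion 7 still binds, so she is not eligible, whatever the note says.
2. **The appendix replaces criterion 7, and item 10 is applied as worded.** She has no highly effective method, so she is not eligible.
3. **The appendix replaces criterion 7, and the note fills only the highly effective part.** One effective method is still owed. The only effective methods listed are barriers, so she needs a third barrier or one of her two must count twice. The text does not say which, so the answer is undetermined.
4. **The appendix replaces criterion 7, and the note satisfies the whole requirement.** She is eligible.

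So she is ineligible on two readings, undetermined on one and eligible on one. Nothing in the documents selects among them. The item numbers do not help: the appendix files items 10 and 11 under Section 5.2.1, whose list ends at 8. By content they correspond to the female and male paragraphs of criterion 7, but correspondence does not show replacement.

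**The case against.** The strongest defence is that the note is a deliberate exception. Item 10 refers to Section 5.2.4, Appendix P supplies its own text under that heading, and the note forms part of that text. On this view item 10 incorporates the note, and a specific qualification governs a general rule. The reading is tenable, but it does not remove the conflict. Neither item 10 nor the two-form sentence signals an exception. The note would accept less than main Section 5.2.4, to which the local rules are described as additional. Whether a further effective method is owed would still be open.

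Other parts of the defence limit how far the point goes:

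- **Enrolment.** A reader might infer that the note lets a site enrol a woman whom the main protocol excludes. The documents do not establish this. If the appendix adds to criterion 7 she stays excluded. If it replaces criterion 7, main Section 5.2.4 no longer sets her minimum. The outcome is conditional.
- **Male subjects.** A reader might infer that the Canadian male-partner rule carries the same ambiguity. Read literally, it does not: it asks for a highly effective method, and the note calls double barrier an alternative to such methods without reclassifying it. Checking that the wording matches is enough.
- **Numbers.** A reader might assume that Canada supplies 5–15% of the 160 subjects and that 30–50% of those are women of childbearing potential. That gives 160 × 0.05 × 0.30 = 2.4 to 160 × 0.15 × 0.50 = 12 women. Both percentages are assumptions, and the result counts every woman under the appendix. The note changes the answer only for those relying solely on double barrier, and the documents have no figure for them.
- **Monitoring.** Women of childbearing potential have urine pregnancy tests at visits from Baseline on, and dosing stops on a positive result. That is relevant context, although testing detects pregnancy and does not prevent it.

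**Conclusion.** The contradiction stands on the wording. Item 10 and the two-form sentence require a highly effective method, main criterion 7 and Section 5.2.4 accept barriers only as an addition to one, and the Appendix P note offers double barrier as an alternative. The eligibility of a double-barrier-only Canadian woman is therefore not determined by the documents.

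The point is narrow. It concerns Canadian sites only, and the number of women affected is not given and may be small or zero. Randomisation, endpoints, power and analysis are unaffected. It merits correction because it leaves an eligibility rule unsettled for a drug that the protocol describes as teratogenic in animals. This conclusion assumes no separate instruction to Canadian sites outside these documents. It takes no view on which contraceptive rule is right.

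**What to change.** Amend Appendix P, and main Section 5.2.4 if needed, as follows:

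- Reconcile the note with item 10, the two-form sentence and main Section 5.2.4, so that one rule decides whether a woman using only double barrier is eligible.
- If double barrier is accepted, state whether a further effective method is still needed.
- State whether items 10 and 11 replace criterion 7 or add to it, and align their numbering with Section 5.2.1.
- Confirm that the male-partner wording matches the rule chosen.

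The choice of rule belongs to the sponsor's clinical and regulatory staff. The cost is amended wording, essentially in one appendix, and an updated eligibility check for Canadian sites. No change to the statistical analysis is needed.

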Appendix Q. Protocol Amendment: List of Changes

The summary of changes is listed in Section 1.1.

Specific Protocol Changes:

Section 6.1.1.3 Adverse Events of Special Interest

Add: new tenth bullet

Decreased lymphocyte counts

Section 8.1.6.2.1 Treatment-Emergent Adverse Events (TEAE)

Eighth paragraph previously read:

The AEs of special interest (including but not limited to serious infections, opportunistic infections, malignancy, hepatic disorder, gastrointestinal perforations, anemia, neutropenia, herpes zoster, creatine phosphokinase (CPK elevation), renal dysfunction, tuberculosis, adjudicated cardiovascular events, cardiac arrhythmias) will be summarized. Event rate (per 100 patient years) for AEs of special interest will also be summarized for the combined safety analysis of Period 1 and Period 2.

Has been changed to read:

- The AEs of special interest (including but not limited to serious infections, opportunistic infections, malignancy, hepatic disorder, gastrointestinal perforations, anemia, neutropenia, herpes zoster, creatine phosphokinase (CPK elevation), decreased lymphocyte counts, renal dysfunction, tuberculosis, adjudicated cardiovascular events, cardiac arrhythmias) will be summarized. Event rate (per 100 patient years) for AEs of special interest will also be summarized for the combined safety analysis of Period 1 and Period 2.

### **3.0 Introduction**

This statistical analysis plan (SAP) describes the statistical analysis to be completed by the AbbVie Data and Statistical Science Department for Upadacitinib study Protocol M16-048 dated 07 June 2017, which incorporates four amendments (original protocol: 24 June 2016; Amendment 1: 25 July 2016; Amendment 2: 18 October 2016; Amendment 3: 16 December 2016; Amendment 4: 07 June 2017). It provides details to further elaborate statistical methods as outlined in the protocol and describes analysis conventions to guide the statistical programming work.

This is the first version of the SAP for Protocol M16-048.

Unless noted otherwise, all analyses will be performed using SAS version 9.2 or later (SAS Institute Inc., Cary, NC 27513) under the UNIX operating system.

### **4.0 Study Objectives, Design and Procedures**

#### **4.1 Objectives**

The primary objective of this study is to evaluate the efficacy of multiple doses of upadacitinib compared with placebo in the treatment of adults with moderate to severe atopic dermatitis (AD). The secondary objectives of this study are to evaluate the safety of upadacitinib compared with placebo as measured by adverse events (AEs), laboratory data, vital signs and Electrocardiogram (ECG).

#### **4.2 Design Diagram**

This is an 88-week Phase 2b, randomized, double-blind, parallel-group, placebo-controlled multicenter study of safety and efficacy of upadacitinib in adult subjects with moderate to severe AD.

The duration of the study will be up to 88 weeks and will include a 35-day maximum screening period, a 16-week double-blind treatment period (Period 1) and a 72-week double-blind treatment period (Period 2). In addition, a 30-day follow-up visit (or phone

---

call if a visit is not possible) should occur to determine the status of any ongoing AEs or serious adverse events (SAEs), or the occurrence of any new AEs/SAEs.

**Period 1:** A 16-week double-blind, placebo-controlled treatment period during which subjects will be randomized in a 1:1:1:1 ratio to one of four treatment groups:

- Group 1: upadacitinib 7.5 mg once daily (QD) for 16 weeks
- Group 2: upadacitinib 15 mg QD for 16 weeks
- Group 3: upadacitinib 30 mg QD for 16 weeks
- Group 4: Matching Placebo for 16 weeks

Randomization will be stratified by geographic region (US/PR/Canada, EU/AUS, and Japan). Enrollment in Japan will be capped at 10% of subjects (4 subjects per group).

In Period 1, discontinuation from study drug will be mandatory for any subject with an Eczema Area and Severity Index (EASI) score worsening of 25% or more compared with their baseline EASI score at any 2 consecutive scheduled study visits from Week 4 to Week 12.

**Period 2:** a 72-week double-blind, placebo controlled treatment period during which subjects who complete Period 1 will be re-randomized at Week 16 within their original treatment group assignments to either upadacitinib or placebo into a 72-week double-blind, placebo controlled treatment period in a 1:1 ratio as shown in [Figure 1](#) (study design). Randomization will be stratified by geographic region and the improvement of EASI score by at least 75% (EASI 75 response) at Week 16. At the Week 16 visit, all subjects will be re-randomized as follows into Period 2:

- Group 1 in Period 1: upadacitinib 7.5 mg QD or matching placebo for 72 weeks
  - Group 2 in Period 1: upadacitinib 15 mg QD or matching placebo for 72 weeks
  - Group 3 in Period 1: upadacitinib 30 mg QD or matching placebo for 72 weeks
-

- Group 4 in Period 1: upadacitinib 30 mg QD or matching placebo for 72 weeks

Starting at the Week 20 visit (4 weeks after re-randomization into Period 2), rescue therapy with upadacitinib 30 mg QD will be provided to subjects who have a first instance of an EASI score improvement of less than 50% (i.e., < EASI 50 response), when compared against the Baseline. These subjects will continue on upadacitinib 30 mg QD for the remainder of the study.

[figure not shown]
During Period 2, concomitant class III – IV, medium potency topical corticosteroid treatment will be permitted at the Week 24 visit and thereafter in subjects after a second instance of < EASI 50 response in any two Period 2 study visits beginning from Week 20 (see Protocol Section 5.2.3.4 for permitted treatments). For subjects who receive topical corticosteroid rescue therapy, a visit will be required 4 weeks after receiving the rescue therapy. Discontinuation from study drug will be mandatory for subjects with < EASI 50 response compared with their baseline EASI score 4 weeks following rescue with topical corticosteroids or at any visit thereafter.

In order to minimize missing data for efficacy and safety assessments, subjects who prematurely discontinue study drug should continue to be followed for all regularly scheduled visits, unless they have decided to discontinue the study participation entirely (withdrawal of informed consent).

A schematic of the overall study design is shown in [Figure 1](#).

